Direct vibration stimulation on the lung surface is not achievable during lung testing. A vibration stimulation on the chest wall causes surface wave propagation on the lung.⁽¹¹⁾

An ultrasonic probe is used to detect the propagation of the tissue wave motion (usually a few micrometers). By indenting a medium and examining the

relationship between the indentation displacement and the generated force, the indentation technique may determine the elasticity of that medium.⁽¹²⁾

A local mechanical vibration on the chest safely generates the surface wave on the lung in LUSWE. Diagnostic ultrasonography is only utilized to identify the propagation of surface waves on the lung. Strain pictures are created by repeatedly applying modest pressure to the tissues using the transducers.^(13, 14)

Following tissue movement is tracked between pairs of echo frames, and strain is determined based on the axial gradient of the displacements. A stiff area endures less strain (deformation) than surrounding softer tissue when subjected to the same amount of force.^(9, 15)

Most hospitalized patients are not able to perform radiological imaging either due to unavailability or inability to ambulate the patients for imaging to be held. We suggested to perform bedside, relatively cheap and available, imaging modality to help in the differentiation between benign and malignant peripheral lung pathologies.

Lung elastography, to be used as diagnostic tool, is considered a new era worldwide; a new modality that will help to reduce the burden and the widespread use of chest computed tomography.⁽¹⁶⁾

AIM OF THE WORK

The aim of this study is to demonstrate the applicability and efficacy of strain elasto-sonographic measurements in differentiating between benign and malignant peripheral parenchymal lesions.

PATIENTS

This study will include patients recruited in cross-sectional sample till achieving requirement of 120 patients with benign and malignant subpleural parenchymal lesions.

Sample size was calculated by medical research institute and biomedical informatics, Medical Statistics Department, Alexandria University.

(APPENDIX A)

Patients enrolled in our study will be examined and investigated in chest department, in Alexandria Main University Hospitals.

Inclusion criteria:

- 1) Adult patients above age of 18 years old.
- 2) Patients with peripheral lung lesion.

Exclusion criteria:

- 1) Pure pleural lesions.
- 2) Clinical instability to reach the final diagnosis.

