- 3) Inaccessibility by ultrasound.

METHODS

This is a diagnostic accuracy study with comparison to gold standard tests e.g., chest computed tomography, transthoracic biopsy, or microbiological analysis. All patients included in this study will give informed consent according to the guidelines of ethics committee, Alexandria Faculty of Medicine. (<http://www.med.alexu.edu.eg/wp-content/uploads/2012/04/Checklist-FINAL-20141.pdf>)

Informed consent is available at (<http://med.alexu.edu.eg/alexuniv/wp-content/uploads/2021/09/Standard-Operating-Procedure-2020-ethics.pdf>).

All patients will be subjected to:

- 1) Thorough history taking.
- 2) Complete physical examination.
- 3) CT scan chest.
- 4) Routine laboratory investigation profile.
- 5) Conventional methods to reach final diagnosis such as microbiological analysis, CT scan, fiberoptic bronchoscopy, and image guided biopsies.
- 6) Strain elastography done by superficial and deep probes, in which B mode is compared with the elastography image for real time assessment; strain ratio is obtained. Strain ratio between benign and malignant peripheral lung lesions to be evaluated.

Data collected from our research aim to estimate a cut-off value by which benign and malignant peripheral parenchymal lesions to be easily discriminated by ultrasonographic elastography.

Statistical methods:

Considering nominal data e.g., clinical features, CT findings, epidemiology, smoking status, and final diagnosis will be statistically analyzed using median, mode, MANN-WHITNEY, and Chi square tests.

While numerical data analysis as arithmetic mean is helpful in situation of age statistical distribution. Strain ratio interpretation, the telltale sign of our study, is directed towards comparison of the cut off value achieved with the final diagnosis of the patients.

Receiver operator characteristic (ROC) curve will be plotted to evaluate and assess the sensitivity and specificity of strain ratio obtained from elastography compared to final diagnosis for 60 of our patients from the total 120 patients recruited in the study.

While according to the remaining 60 patients, a multivariate Cox proportional hazard analysis would be held to validate and evaluate results obtained from the former 60 examined patients.

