At the end of the study, sensitivity, specificity, area under the curve (AUC), accuracy of a certain cut-off value, positive predicted value (PPV) and negative predicted value (NPV) would describe the performance of strain ratio as a diagnostic tool in the main aim of the research.

ETHICS OF RESEARCH

Research on human or human products:

- Prospective study: Informed consent will be taken from patients. In case of incompetent patients, the informed consent will be taken from the guardians.
- Retrospective study: Confidentiality of records will be considered
- DNA / genomic material: Informed consent for DNA / genomic test and research will be taken from patients. No further tests will be carried out except with further approval of committee and patients. If the samples will travel outside Egypt, the researcher will be responsible for transportation and security approval.
- All drugs used in the research are approved by the Egyptian Ministry of Health

Research on animal:

- The animal species are appropriate for the test.
- After test, if the animal will suffer, it will be euthanized and properly disposed.
- After operation, it will have a proper postoperative care.

سأقوم بتسلیم الموافقات المبنیة على علم المريض الخاصة بالدراسة عند الانتهاء منها او عند طلبها
من اللجنة

RESULTS

The results obtained from this study will be tabulated and statistically analyzed using appropriate statistical methods and appropriate figures and diagrams.

DISCUSSION

The results obtained from this study will be discussed in the view of achievement of the aim and will be compared with any of the available published data in the same field of the research.

REFERENCES

1. Beach KW. 1975-2000: a quarter century of ultrasound technology. *Ultrasound Med Biol*. 1992;18(4):377-88.
2. Volpicelli G. Lung sonography. *J Ultrasound Med*. 2013;32(1):165-71.

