APPENDIX A

Alexandria University
Medical Research Institute
Biomedical Informatics &
Medical Statistics Department

Name: [name]

Sample Size Calculation

The main aim of this study is to demonstrate accuracy of elastosonographic measurements in differentiating benign vs malignant subpleural parenchymal lesions compared to clinical, radiological (CT/PET). A recent study concluded that the ROC curve elaborated for the diagnosis of malignancy by strain elastography showed an AUC of 0.688. ⁽¹⁾ Consequently, patients will be recruited in a cross-sectional sample till achieving the minimum required sample of 60 patients with benign vs 60 patients with malignant subpleural parenchymal lesions with 80% power.

Sample size was calculated using a two-sided, ROC curve test at .05 significance level using R software.

Program Citation:

R Core Team (2017). R: A language and environment for statistical computing. R Foundation for Statistical Computing, Vienna, Austria. URL <https://www.R-project.org/>.

Reference:

Calculated and reported by: [name] [name]
Assistant Professor of Medical Statistics, systematic reviews and Evidence Synthesis. Medical Statistics Department, Medical Research Institute-Alexandria University
Email: [contact]. LinkedIn: [name].
[contact]

[name] [name]
IMAS
26/3/2022

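### The second 60 patients are to validate the ROC result by Cox regression, which does not fit a cross-sectional binary diagnosis, and no independent test of the cut-off is specified

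*Combined protocol and SAP*

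**What the plan says.** - **Design.** METHODS states: "This is a diagnostic accuracy study with comparison to gold standard tests". PATIENTS states: "This study will include patients recruited in cross-sectional sample till achieving requirement of 120 patients".
- **Goal.** METHODS, before the statistical section: "Data collected from our research aim to estimate a cut-off value by which benign and malignant peripheral parenchymal lesions to be easily discriminated".
- **First 60.** Under Statistical methods, a ROC curve assesses the sensitivity and specificity of the strain ratio "compared to final diagnosis for 60 of our patients from the total 120 patients recruited in the study".
- **Second 60.** The next sentence says that in the remaining patients "a multivariate Cox proportional hazard analysis would be held to validate and evaluate results obtained from the former 60 examined patients". No covariates are named for this model.
- **Use of the cut-off.** Interpretation of the strain ratio "is directed towards comparison of the cut off value achieved with the final diagnosis of the patients".
- **Final measures.** The section closes with "At the end of the study, sensitivity, specificity, area under the curve (AUC), accuracy of a certain cut-off value", followed by PPV and NPV. It does not say in which patients these are computed.
- **Sample size.** Appendix A takes an AUC of 0.688 from a published study and asks for a "minimum required sample of 60 patients with benign vs 60 patients with malignant subpleural parenchymal lesions with 80% power".

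**The concern.** The plan sets half the sample aside to validate the other half, and then names a survival model to do it. The data to be collected are one strain ratio and one diagnosis per patient. There is no survival outcome for the model to work on, and its output would not be a sensitivity, a specificity or an AUC.

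Without that analysis, the plan has no defined step that tests the cut-off in patients who played no part in choosing it. The cut-off and its accuracy are the main product of the study. Accuracy measured in the patients who set the cut-off is biased upwards, and the plan leaves open whether such patients are in the reported figures.

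**Working it through.** **1. What Cox regression needs, against what the plan defines**

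| Needed | In the document |
|---|---|
| Time origin | None |
| Follow-up time | None; sampling is cross-sectional |
| Event and censoring indicator | None; the outcome is benign or malignant at final diagnosis |
| Covariates for a multivariable model | None assigned |

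No calculation for the Cox analysis can be attempted, since there is no event count, hazard ratio or follow-up to put into one.

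**2. What independent validation of a cut-off needs, against what the plan defines**

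| Needed | In the document |
|---|---|
| Separate patients | Yes, 60 and 60 |
| Rule for allocating patients to the halves | Not stated |
| Rule for choosing the cut-off in the first half | Not stated |
| Cut-off applied unchanged in the second half | Not stated |
| Patients from whom final accuracy is reported | Not stated |

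The 60 + 60 in Appendix A is by diagnosis; the 60 + 60 in Statistical methods is by analysis role. They must be kept distinct: a split by diagnosis would leave the ROC set with one class only.

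**3. Size of the possible optimism**

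The plan gives no figure for its validation step, so there is none to reproduce. The sample size in Appendix A is not used beyond its counts.

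- From the document: AUC 0.688; 60 benign and 60 malignant.
- Assumed: cut-off maximises the Youden index; equal-variance binormal model; 30 benign and 30 malignant in each half.
- Separation of the two distributions: d = √2 × z(0.688) = 0.693.
- Best achievable mean of sensitivity and specificity: Φ(d/2) = Φ(0.347) = 63.6%.

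Mean of sensitivity and specificity over 20,000 simulated studies:

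| Patients reported | Reported | True in new patients | Excess (points) |
|---|---|---|---|
| (a) First 60 only | 68.4% | 62.2% | 6.2 |
| (b) Cut-off chosen and reported on all 120 | 66.9% | 62.6% | 4.2 (before rounding) |
| (c) First-60 cut-off reported on all 120 | 65.3% | 62.2% | 3.1 |
| (d) First-60 cut-off reported on second 60 only | 62.2% | 62.2% | 0 |

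Row (c) follows from (a) and (d): (68.4 + 62.2)/2 = 65.3. A separate run of 4,000 studies gave a Youden index J of 0.370 apparent against 0.244 true for a 30/30 derivation set. Since the mean of sensitivity and specificity is (1 + J)/2, that is 68.5% against 62.2%, in agreement with row (a).

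True performance is about 12.2 points above the 50% of a useless test. The excess in (c) to (a) is therefore 3.1/12.2 = 25% to 6.2/12.2 = 51% of the real gain.

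Varying the assumptions (6,000 studies each), excess in points for (a), (b), (c):

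| Setting | (a) | (b) | (c) |
|---|---|---|---|
| First half 20/40 or 40/20, AUC 0.688 | 6.7 | 4.2 | 3.0 |
| 30/30, AUC 0.75 | 5.8 | 3.9 | 2.9 |
| 30/30, AUC 0.80 | 5.4 | 3.7 | 2.7 |

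The AUC uses no cut-off and shows no optimism: its mean was 0.688 in the first 60, the second 60 and all 120.

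**4. Precision of the two possible repairs**

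- Exact 95% CI for 21/30 (70%): 50.6% to 85.3%.
- Exact 95% CI for 42/60 (70%): 56.8% to 81.2%.
- Bootstrap optimism correction on all 120 (800 studies, 100 resamples each): apparent 66.8%, corrected 63.9%, true 62.6%. The residual is 63.9 − 62.6 = 1.3 points.

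**The case against.** The strongest case on the other side has five parts.

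- **Cox can be made to run.** With a constant time for everyone and malignancy as the event, software returns a coefficient. That is true, but the plan describes no such device, and the coefficient would still say nothing about sensitivity or specificity at a cut-off.
- **The intent to validate is stated.** This stands. The plan sets aside separate patients to check the ROC results. What is missing is a usable method, a locked cut-off and the reporting set.
- **Allocation is not wholly silent.** The word former, applied to the first 60 examined, could mean order of examination. It could equally mean the group mentioned first, so a clear statement is still needed.
- **The bias may be nil.** A team that reports only the second 60 has no optimism, and 6 points is the least favourable reading. This is right, and the size is therefore given by reporting set. The plan permits every one of these readings, including those that flatter the test.
- **Split-sample is not clearly the better estimator.** The held-out estimate has a standard deviation of about 6 points. Choosing and reporting on all 120 has a bias of about 4 and a standard deviation of about 4, a total error of √(4² + 4²) ≈ 5.7. This is fair, and is why optimism-corrected use of all 120 is an acceptable alternative.

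One further remark stands: recruiting towards 60 benign and 60 malignant sets prevalence near 50% by design, so PPV and NPV describe that mix.

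**Conclusion.** The concern holds. The only analysis named for validation needs time-to-event data that this study does not define, and it would not confirm a cut-off even if a fit were forced. No other sentence supplies the missing test: the list of final measures names no patient set, and the general promise of appropriate statistical methods under RESULTS does not replace the named analysis.

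The consequence is an overstatement of the mean of sensitivity and specificity of about 6, 4, 3 or 0 points, depending on which patients are reported. Those sizes rest on the assumed Youden rule, binormal model and 30/30 halves. For the three optimistic reporting sets they range from about 2.7 to 6.7 points over the alternatives tried. The mismatch between Cox regression and the data rests on no numerical assumption. Because it concerns the study's main result, it should be corrected before any analysis.

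**What to change.** Replace the Cox sentence and complete the section as follows.

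1. Delete the Cox analysis.
2. State, before any analysis, how patients are allocated to the two halves, for example by enrolment order or at random stratified by final diagnosis.
3. Name the rule that sets the strain-ratio cut-off in the first 60, and state that this cut-off is applied unchanged to the remaining 60.
4. Report sensitivity, specificity, PPV, NPV and AUC in the second 60, with 95% CIs, as the headline accuracy. Note that PPV and NPV reflect the enrolled mix of benign and malignant lesions.
5. As an acceptable alternative to the split, use all 120 with bootstrap or cross-validated optimism correction, and say so in advance.
6. If an adjusted analysis is wanted, use logistic regression with malignant or benign as the outcome and covariates named beforehand.

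The cost is three or four sentences, with no extra patients, data or procedures. Reported accuracy will look slightly less favourable. Validation in 60 is imprecise (51% to 85% for 21/30). The all-120 route is tighter (57% to 81% for 42/60) but may leave about 1 point of optimism.

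### Minima of 60 benign and 60 malignant fit a total of 120 only at exactly 60/60; if that split is enforced, raw PPV, NPV and accuracy on all 120 carry a 50% prevalence set by design, and no adjustment is planned

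*Combined protocol and SAP*

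**What the plan says.** Three places bear on who is recruited.

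- Appendix A, Sample Size Calculation: "patients will be recruited in a cross-sectional sample till achieving the minimum required sample of 60 patients with benign vs 60 patients with malignant" lesions. These are minima for each group.
- PATIENTS: patients are "recruited in cross-sectional sample till achieving requirement of 120 patients with benign and malignant subpleural parenchymal lesions". No split is given, and the section refers to Appendix A for the calculation.
- METHODS, Statistical methods: the ROC curve uses 60 patients "from the total 120 patients recruited in the study", and the remaining 60 are used for validation. How the two halves are formed, and their make-up by diagnosis, is not stated.

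The last paragraph of Statistical methods lists sensitivity, specificity, AUC and accuracy, and then says that "positive predicted value (PPV) and negative predicted value (NPV) would describe the performance of strain ratio as a diagnostic tool". It does not say whether these come from all 120 patients or from one half. The document states no malignancy rate, no target prevalence, no adjustment of predictive values to a prevalence, and no likelihood ratios. It describes no quota, no cap on either group, and no rule for when one group fills first.

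**The concern.** PPV and NPV depend on the share of malignant lesions in the set analysed; so does accuracy whenever sensitivity and specificity differ. If that share is fixed by the sample-size target, a single raw PPV and NPV describes a population in which half the lesions are malignant, whatever the real rate is.

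This matters because the introduction gives the test a clinical use: "We suggested to perform bedside, relatively cheap and available, imaging modality to help in the differentiation between benign and malignant peripheral lung pathologies". A clinician who reads a published PPV is likely to take it as the chance of malignancy in a patient with a positive result. Under an enforced 60/60 split it has that meaning only where about half of such patients have malignancy. Sensitivity, specificity and AUC are not affected in this way.

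**Working it through.** **1. The plan's own figure.** With B benign and M malignant patients, Appendix A requires B ≥ 60 and M ≥ 60, and the other two sections give B + M = 120. Since 60 + 60 = 120, there is no slack. The only solution is B = M = 60, a malignant fraction of 60/120 = 50%.

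**2. What recruitment without a quota would give.** The true malignant share p is not in the documents, so values are assumed.

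| p | Chance of exactly 60/60 in 120 | Mean size of smaller group in 120 | Mean total until both groups reach 60 |
|---|---|---|---|
| 0.5 | 0.073 | 56 | 129 |
| 0.6 | 0.006 | 48 | 150 |
| 0.7 | below 0.0001 | 36 | 200 |

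The first column is the binomial probability C(120,60) p^60 (1−p)^60. If recruitment runs on until both minima are met, the sample's malignant fraction stays close to p (simulated means 0.499, 0.597 and 0.696).

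**3. Size of the prevalence effect (illustration).** Input from Appendix A: AUC 0.688. Assumptions: an equal-variance binormal curve and a symmetric cut-off.

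- Separation d = √2 × z(0.688) = 0.693, so sensitivity (se) = specificity (sp) = Φ(0.693/2) = 0.636.
- PPV = se·p / [se·p + (1−sp)(1−p)]
- NPV = sp(1−p) / [sp(1−p) + (1−se)p]

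| Malignant share | PPV | NPV |
|---|---|---|
| 30% | 0.43 | 0.80 |
| 50% | 0.64 | 0.64 |
| 70% | 0.80 | 0.43 |

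Accuracy = se·p + sp(1−p). It does not move when se = sp. On the same curve with se = 0.80, sp = Φ(0.693 − z(0.80)) = 0.441, and accuracy is 0.55, 0.62 and 0.69 at 30%, 50% and 70%.

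**4. Comparison with sampling error, with 60/60 fixed.** On the logit scale, SE = √[(1−se)/(60·se) + sp/(60(1−sp))] = 0.197. The 95% half-width of PPV at 50% is 1.96 × 0.197 × 0.636 × 0.364 = 0.09. A simple binomial half-width on 60 test-positives, 1.96√(0.636 × 0.364/60) = 0.12, does not fit this reading because the group sizes are fixed.

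The likelihood ratio of a positive result is 0.636/0.364, or 1.744 before rounding. PPV differs from 0.636 by 0.089 at these points:

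- PPV 0.546: odds 1.204; 1.204/1.744 = 0.691; p = 0.691/1.691 = 0.41.
- PPV 0.725: odds 2.633; 2.633/1.744 = 1.510; p = 1.510/2.510 = 0.60.

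So the prevalence error in PPV exceeds sampling error below about 41% or above about 60% malignant. By symmetry, the limits for NPV are about 40% and 59%. At 30%, the Bayes-rule PPV from 60/60 data is 0.43 (95% CI 0.34 to 0.52), which excludes the raw 0.64.

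**5. What does not move.** The Hanley-McNeil standard error of the AUC at 0.688 is 0.048, 0.048 and 0.050 for splits of 60/60, 72/48 and 84/36.

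**The case against.** A reader might infer that the study is a case-control design whose predictive values are fixed at 50% prevalence. The documents do not support that. Both PATIENTS and Appendix A call the sample cross-sectional, and neither mentions a quota or separate sampling of the two groups. PATIENTS points to Appendix A, so 120 can be read as the sum of two minima and not as a ceiling, although the fixed total in Statistical methods tells against this. Without a quota the malignant fraction is simply the observed one. This objection stands, and it makes the point conditional.

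A reader might also infer that 50% follows once 60/60 is enforced. It does not if PPV and NPV come from one half, because the rule for forming the halves is not stated. The reference to the end of the study suggests all 120 but does not settle it. In a half with about 30 test-positives, the simple binomial half-width would be 1.96√(0.636 × 0.364/30) = 0.17, so sampling error would hide more of any prevalence effect.

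Nor do the documents show that the error is large: they give no malignancy rate. Sensitivity and specificity will be reported alongside, so a careful reader could compute a local PPV.

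Finally, even a consecutive sample may not match the intended users. The introduction speaks of inpatients who cannot have imaging, while METHODS gives every participant a CT scan and PATIENTS excludes those too unstable to reach a diagnosis. This too stands: it is a reason to show the malignant fraction under every reading.

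**Conclusion.** The point holds in conditional form. The recruitment statements agree only at exactly 60/60, which 120 consecutive patients would rarely produce. What follows depends on the reading:

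- **60/60 enforced, all 120 analysed:** PPV, NPV and accuracy carry a 50% prevalence by design.
- **One half analysed:** the malignant fraction is whatever the unstated split gives.
- **Consecutive, no quota:** the prevalence objection largely falls away, but either the total of 120 or the 60-per-group minimum will usually not hold.

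Under the first reading, the illustration moves PPV by about 0.2 if the true share is 30% or 70% (0.636 − 0.428 = 0.208; 0.803 − 0.636 = 0.167). It stays within sampling error between about 41% and 60%. This rests on the assumed curve, cut-off and prevalence range; the actual size and direction are unknown. Severity is low, because the sample size rests on AUC, which is not affected.

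**What to change.** 1. In the last paragraph of Statistical methods: if a 60/60 split is enforced, replace the single raw PPV and NPV with values computed by Bayes' rule from the estimated sensitivity and specificity over a stated prevalence range (for example 20% to 80%), with confidence intervals.
2. In every case, show the malignant fraction of the analysed set beside any raw PPV, NPV or accuracy, and say whether all 120 patients or one half supplies them.
3. As a secondary step, reconcile PATIENTS, Statistical methods and Appendix A: say whether 60/60 is a quota and, if not, whether the total or the minima give way.

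The reporting change costs wording and one table, needs no extra patients, and may make PPV or NPV look less favourable. The recruitment decision can cost more. Group membership may be known only after the work-up in METHODS ("Conventional methods to reach final diagnosis such as microbiological analysis, CT scan, fiberoptic bronchoscopy, and image guided biopsies"), so filling 60/60 would mean assessing about 129, 150 or 200 patients on average at 50%, 60% or 70% malignant, of whom about 9, 30 or 80 would not be analysed. Consecutive recruitment that keeps both minima needs the same totals but analyses everyone. Stopping at 120 adds no patients but usually leaves one group below 60.
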